- Composite neonatal outcome comprised of fetal or neonatal death or RDS, Grade 3 or 4 IVH, PVL, Stage 2 or 3 NEC, BPD, Stage III or higher ROP, or early onset sepsis. Occurrence of any of the individual components is considered indicative of the outcome
- Length of hospital stay, need for NICU or intermediate care admission and length of stay if admitted

5 Statistical Considerations

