5.2 Sample Size and Power

A one-third reduction in preterm birth < 35 weeks was selected as being clinically meaningful. It is assumed that pessary and micronized progesterone are more likely to be effective for preventing spontaneous rather than indicated preterm birth. If 20% of the preterm births at this gestation are indicated (lower than that typically expected since these women will all have a short cervix) and if there is a 40% reduction in spontaneous preterm birth and no reduction in indicated preterm birth, then the overall effect size would be slightly less than a one-third reduction in all preterm births.

Table 3 below shows the sample sizes required to detect 30-33% reduction in PTB < 35 weeks if the rate in the placebo group is 50-60%, with type I error 2.5% 2-sided and power of 90%. Type I error was chosen to be 2.5% 2-sided since there will be two primary comparisons (between pessary and placebo and between progesterone and placebo).

Table 3. Sample Sizes per Group for Different Primary Outcome Rates, Power and Effect Sizes²

Reduction in Primary Outcome Rate	% Power	Primary Outcome Rate in Placebo Group		
		50%	55%	60%
30%	80	210	180	150
	85	240	200	170
	90	270	230	190
33.3%	80	170	140	120
	85	190	160	140
	90	220	190	160

²Rounding up to next 10

In STTARS, women were given a test injection of progesterone (17- α hydroxyprogesterone caproate) and asked to return for randomization in three days or more. A total of 2.7% of women did not return or withdrew consent. Since a compliance run-in such as this is not feasible for PROSPECT, it is assumed conservatively that as many as 5% of the women drop out and effectively become crossovers. This would require an adjustment in the sample size of approximately 10.8%. Thus, adjusting for 5% crossover, a sample size of 630 patients is sufficient to detect a one-third reduction in the primary outcome rate of 55% in the placebo group with 90% power for either the pessary or the progesterone arm, and at least 80% power if the effect size is as low as 30%.

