- Bacterial vaginosis/Nugent score at enrollment—Nugent ≥ 7 with pH > 4.4
- Fetal fibronectin positive
- Type of conception/use of ART
- Prior cervical surgery including LOOP/ LEEP

Loss to follow-up will be defined as no information regarding pregnancy prior to 35 weeks. Those defined as lost to follow-up will not be included in the primary analysis. It is expected that the loss to follow-up rate will be very low. For trials conducted by the MFMU Network, the loss to follow-up rate has typically been under 2 percent. However, a sensitivity analysis will be performed including patients lost to follow-up with different assumptions regarding their outcome, to determine whether the results are robust.

Since many of the secondary endpoints are dichotomous variables like the primary outcome, standard statistical methods for rates and proportions will be appropriate. The Wilcoxon rank sum test will be used to compare continuous variables, and survival analysis methodology will be used to compare time-to-event variables, such as time to delivery or fetal demise and gestational age at delivery or fetal demise.

In general, analyses of data will be conducted to address the primary and secondary research questions of the trial, and other interrelationships among elements of study data of interest to the investigators and of relevance to the objectives of the study.

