6.1 Data Collection Forms

Data will be collected on standardized forms on which nearly all responses have been pre-coded. Each form is briefly described below:

- PR01 Screening Log.
- PR01A Eligibility Checklist
- PR02 Eligibility and Randomization Form is completed for all patients eligible for the study.
- PR03 Study Drug Randomization Log: lists patients randomized to progesterone or placebo, and provides the drug code number.
- PR03A Pessary Accountability Log lists the specific pessary(ies) given to each patient.
- PR04 Baseline Form is completed for all randomized patients. This form includes detailed demographic and social data, medical and obstetrical history, and current pregnancy complications.
- PR04A Previous Pregnancy Outcome Form.
- PR05 Study Visit Form documents monthly study visits, possible side effects and compliance
- PR06 Study Drug Dispensing and Compliance Log documents the dispensing of study medication and the return of any unused study medication.
- PR06A Study Drug Final Use Form documents the reason for stopping study drug.
- PR07 Unscheduled Visit or Hospitalization Form is completed for all patients who had an unscheduled emergency room, Labor & Delivery, clinic visit or hospitalization between the scheduled monthly visits, including the delivery admission.
- PR08 Maternal Delivery and Outcome Form documents specific pregnancy complications since randomization, in addition to labor, delivery and postpartum information.
- PR09 Neonatal Baseline Form records date and time of birth, delivery data and status at delivery, for each fetus/infant.
- PR10 Neonatal Outcome Form records outcome data for all infants admitted to the NICU or special care nursery.
- PR11 Patient Status Form documents loss to follow up/withdrawal status, last date of contact for lost to follow-up patients, side effects since the last dose.
- PR12 Adverse Event Form records serious and non-serious adverse events.
- PR13A Women's Views on the Arabin Pessary, a patient questionnaire.
- PR13B Women's Views on the Study Medication, a patient questionnaire.
- PR14 Pessary Removal Form documents the position of the pessary at the time of removal.

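### Section 5.5 names only independent-sample tests for secondary outcomes, without fixing the unit of analysis for infant-level neonatal outcomes or allowing for correlation between co-twins

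*Combined protocol and SAP*

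**What the plan says.** Section 5.5 (Analysis Plan) covers the secondary outcomes in two sentences. For binary outcomes: "Since many of the secondary endpoints are dichotomous variables like the primary outcome, standard statistical methods for rates and proportions will be appropriate". For the others: "The Wilcoxon rank sum test will be used to compare continuous variables", with survival methods for time-to-event variables.

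Section 4.7.3 lists the fetal and neonatal outcomes. Several definitions refer to the individual infant: small for gestational age uses that infant's sex and race, bronchopulmonary dysplasia has a criterion for infants born before 32 weeks, and sepsis requires the infant to be clinically ill. Ventilator time, oxygen time and length of stay are also listed. The composite is introduced as "Composite neonatal outcome comprised of fetal or neonatal death or RDS" and further components, and any one component counts. The section does not say whether that means in one infant or in the pregnancy.

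The forms in Section 6.1 are organised by infant. The neonatal baseline form "records date and time of birth, delivery data and status at delivery, for each fetus/infant". The neonatal outcome form covers infants admitted to the NICU or special care nursery.

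Sections 4.7.1 and 4.7.2 are different. The primary outcome and the preterm-delivery outcomes count an event in either twin, and another maternal outcome requires at least one liveborn infant. Those rules give one result per pregnancy. Section 4.7.3 has no such rule.

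**The concern.** A simple comparison of proportions suits the primary outcome because each randomized woman contributes one result, not because the outcome is binary. Section 5.5 extends the method to other outcomes on the ground that they too are binary, and that ground is not sufficient. Co-twins share a mother, an assigned treatment and usually a gestational age at birth, so positive correlation between their outcomes is plausible. Since both twins are always in the same arm, positive correlation raises the variance of the arm comparison, and a test that ignores it gives intervals that are too narrow.

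Section 3.2 puts neonatal morbidity or mortality first among the secondary outcomes in question. Sections 2.3 and 2.4 cite neonatal composite results as part of the rationale for the trial. Under Section 6.4, reports to the data and safety monitoring committee include all outcome variables. An understated standard error could therefore make chance look like neonatal benefit or harm, in the final report or during monitoring.

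**Working it through.** **Inputs from the documents**
- 630 women allocated 1:1:1 (Sections 3.3 and 3.6), so 210 women and up to 420 fetuses or infants per arm.
- Placebo rate 55%, one-third reduction to 36.7%, 90% power, 5% crossover (Section 5.2).
- Alpha for the primary comparisons: "Type I error was chosen to be 2.5% 2-sided since there will be two primary comparisons". No alpha is stated for secondary outcomes, so 5% is used below and 2.5% is also checked.

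**Assumed input.** The within-pair correlation (ICC) is not given. The range 0.1 to 0.9 is shown.

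**Step 1: reproduce the plan's own figure.** The pooled-variance formula without continuity correction is

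n = [z(0.9875)·√(2·p̄·(1−p̄)) + z(0.90)·√(p1(1−p1) + p2(1−p2))]² / (p1−p2)²

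With p1 = 0.55, p2 = 0.3667 and p̄ = 0.4583:

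n = (2.2414 × 0.7046 + 1.2816 × 0.6926)² / 0.1833² ≈ 181.1, so 182 per group, or 190 after the plan's rounding up to the next 10.

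Crossover adjustment: 190 / 0.95² = 210.5 per arm; 3 × 210.5 = 631.6, against 630 stated. The figure reproduces. It concerns an outcome with one result per pregnancy, so nothing below changes it.

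**Step 2: effect of ignoring the pairing.** For clusters of two, the design effect is 1 + (2−1)·ICC = 1 + ICC. If infants are treated as independent:
- SE understatement = 1 − 1/√(1 + ICC)
- true size at nominal 5% = 2·[1 − Φ(1.96/√(1 + ICC))]
- true coverage of a nominal 95% interval = 1 − true size

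Example, ICC 0.5: 1.96/√1.5 = 1.600, giving a size of 0.110.

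| Assumed ICC | SE too small by | True size, nominal 5% | True coverage, nominal 95% |
|---|---|---|---|
| 0.1 | 5% | 6.2% | 93.8% |
| 0.3 | 12% | 8.6% | 91.4% |
| 0.5 | 18% | 11.0% | 89.0% |
| 0.7 | 23% | 13.3% | 86.7% |
| 0.9 | 27% | 15.5% | 84.5% |

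**Step 3: when the error rate doubles.** At nominal 5%, set 1.96/√(1 + ICC) = 1.645. Then ICC = (1.96/1.645)² − 1 ≈ 0.42. At nominal 2.5%, ICC = (2.2414/1.96)² − 1 ≈ 0.31.

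**Step 4: simulation check.** 210 pairs per arm, no treatment effect, 40,000 replicates, nominal 5%. Each cell gives the rejection rate at a 10% / 30% event rate.

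| ICC | Infants as independent | Variance clustered on mother | One either-twin result per pregnancy |
|---|---|---|---|
| 0 | 0.051 / 0.050 | 0.052 / 0.050 | 0.051 / 0.045 |
| 0.3 | 0.086 / 0.085 | 0.051 / 0.050 | 0.050 / 0.050 |
| 0.5 | 0.110 / 0.110 | 0.050 / 0.051 | 0.050 / 0.052 |
| 0.7 | 0.133 / 0.132 | 0.049 / 0.051 | 0.048 / 0.049 |
| 0.9 | 0.157 / 0.156 | 0.051 / 0.051 | 0.050 / 0.052 |

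The simulation agrees with the formula. Both remedies hold the size near 5%.

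**Limits.** The formula assumes that both twins contribute to the outcome. Where only liveborn infants are assessed, some women contribute one infant and the inflation is smaller. One ICC will not fit outcomes as different as respiratory distress, small for gestational age and sepsis. The simulation covers binary outcomes; the rank sum test was not simulated.

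**The case against.** The strongest reply is that the plan nowhere says infants will be treated as independent. Section 5.5 bases all analyses on the randomized patients, who are women. The sentence on binary outcomes takes the primary outcome as its model, and that outcome has one result per pregnancy. It speaks of many secondary endpoints without naming the neonatal ones, and Section 4.7.2 has many binary outcomes at the level of the woman. Recording data by infant does not settle the unit either, since an either-twin outcome also needs data on each fetus. Read as one result per pregnancy, Section 5.5 is valid for binary outcomes as written.

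This stands as far as it goes. A reader might infer that the plan prescribes an invalid test, so that standard errors will be too small and false positives will double. The documents do not support that: the unit is unstated, the ICC is not given, and at ICC 0.1 to 0.3 the error rate rises by a factor of 1.2 to 1.7. Nor is every item in Section 4.7.3 an infant outcome; twin-twin transfusion syndrome belongs to the pregnancy. The documents also give the neonatal composite no key-secondary status.

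The reply does not close the gap. Section 4.7.3 mostly defines outcomes on the infant and lacks the pregnancy-level wording used in Sections 4.7.1 and 4.7.2. Applying the named methods to those outcomes as defined ignores the pairing. The per-pregnancy reading leaves other matters open: whether one or both infants must be affected, and how two durations become one value. Those choices could then be made after results are known.

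**Conclusion.** The point holds in conditional form. Section 5.5 names only independent-sample methods, while most Section 4.7.3 outcomes are defined on infants who come two to a randomized woman; the unit of analysis is not fixed and co-twin correlation is not provided for. The error rates in the table above apply only if infants are analysed as independent and the ICC is positive, and their size rests on assumed ICCs.

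The consequence is confined to secondary outcomes. Both primary comparisons have one result per woman and stand as planned. This is a should-fix item: the named methods are wrong under one natural reading and incomplete under the other.

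**What to change.** In Section 5.5, assign each Section 4.7.3 outcome to one of two routes before treatment comparisons are seen:

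- **Infant level, variance clustered on the mother.** For binary outcomes, use modified Poisson or log-link GEE with robust variance, reporting relative risks and confidence intervals. For durations, use a clustered rank sum test or a bootstrap that resamples mothers.
- **One result per pregnancy, by an explicit rule.** For example, count a binary outcome if either infant is affected, and state how two durations are combined. The standard methods already named then apply.

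Either route is sound, but they answer different questions (risk per infant, or risk per pregnancy), so the choice should be stated for each outcome and, in particular, for the composite. The same rule should govern the tables sent to the data and safety monitoring committee.

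The cost is a paragraph of text and standard software, with no new data. Infant-level intervals become wider than those from an analysis that ignores pairing, by a factor of √(1 + ICC): about 1.05 at ICC 0.1 and 1.38 at ICC 0.9. That extra width is uncertainty the naive interval would have left out.

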5.5.1 Racial/Ethnic Subgroup Analysis

The racial/ethnic composition of women recruited into the MFMU Network trials varies. Assuming for this trial that the composition is 20% African-American and 15% Hispanic, similar to the STTARS trial there is limited power (50% or less) to detect a 50% reduction in the primary outcome in the separate subgroups.

6 Data Collection

6.1 Data Collection Forms

Data will be collected on standardized forms on which nearly all responses have been pre-coded. Each form is briefly described below:

- PR01 Screening Log.
- PR01A Eligibility Checklist
- PR02 Eligibility and Randomization Form is completed for all patients eligible for the study.
- PR03 Study Drug Randomization Log: lists patients randomized to progesterone or placebo, and provides the drug code number.
- PR03A Pessary Accountability Log lists the specific pessary(ies) given to each patient.
- PR04 Baseline Form is completed for all randomized patients. This form includes detailed demographic and social data, medical and obstetrical history, and current pregnancy complications.
- PR04A Previous Pregnancy Outcome Form.
- PR05 Study Visit Form documents monthly study visits, possible side effects and compliance
- PR06 Study Drug Dispensing and Compliance Log documents the dispensing of study medication and the return of any unused study medication.
- PR06A Study Drug Final Use Form documents the reason for stopping study drug.
- PR07 Unscheduled Visit or Hospitalization Form is completed for all patients who had an unscheduled emergency room, Labor & Delivery, clinic visit or hospitalization between the scheduled monthly visits, including the delivery admission.
- PR08 Maternal Delivery and Outcome Form documents specific pregnancy complications since randomization, in addition to labor, delivery and postpartum information.
- PR09 Neonatal Baseline Form records date and time of birth, delivery data and status at delivery, for each fetus/infant.
- PR10 Neonatal Outcome Form records outcome data for all infants admitted to the NICU or special care nursery.
- PR11 Patient Status Form documents loss to follow up/withdrawal status, last date of contact for lost to follow-up patients, side effects since the last dose.
- PR12 Adverse Event Form records serious and non-serious adverse events.
- PR13A Women's Views on the Arabin Pessary, a patient questionnaire.
- PR13B Women's Views on the Study Medication, a patient questionnaire.
- PR14 Pessary Removal Form documents the position of the pessary at the time of removal.

6.2 Web Data Entry System

For this protocol, web data entry screens corresponding to the study forms listed above will be developed and maintained by the staff of the BCC. Clinical center staff will enter data into the MySQL database located at the BCC through a web data management system (MIDAS). The data are edited on-line for missing, out of range and inconsistent values. A Users' Manual documenting this system is provided to the centers by the BCC.

6.3 Centralized Data Management System

Daily data conversions from the MySQL database create up-to-date SAS datasets. Data are reviewed weekly using edit routines similar to those implemented on-line during data entry, as well as additional checks for data consistency within or across forms. A database of resulting potential data problems is generated in MIDAS for initial review by BCC staff who then evaluate the comments keyed in association with edits on missing or unusual values. Valid edits will be flagged in MIDAS for resolution at the clinical centers.

At regular intervals, specialized data reviews comparing data availability and consistency across forms are run by the BCC staff on the entire database or on a specific subset of data. These reports are also submitted to the centers for correction or clarification.

An audit trail, consisting of all prior versions of each data form as entered in the computer for each patient, is maintained so that the succession of corrections can be monitored.

6.4 Performance Monitoring

The BCC will present regular reports to the PROSPECT Subcommittee, the Steering Committee, and the Data and Safety Monitoring Committee. These include:

- Monthly Recruitment Reports - reports of the number of women screened and enrolled by month and by clinical center are provided monthly to the PROSPECT Subcommittee and all other members of the Steering Committee. Weekly or bi-weekly reports are provided electronically if needed.
- Quarterly Steering Committee Reports - reports detailing recruitment, baseline patient characteristics, data quality, incidence of missing data and adherence to study protocol by clinical center, are provided quarterly to the PROSPECT Subcommittee and all other members of the Steering Committee.

Data and Safety Monitoring Committee Reports - for every meeting of the DSMC, a report is prepared which includes patient recruitment, baseline patient characteristics, center performance information with respect to data quality, timeliness of data submission and protocol adherence (in addition to safety and efficacy data). The reports also include adverse events, loss to follow-up and all outcome variables as described previously in this protocol.

7 Study Administration

7.1 Organization and Funding

The study is funded by the *Eunice Kennedy Shriver* National Institute of Child Health and Human Development (NICHD). The study is conducted by the NICHD Maternal-Fetal Medicine Units (MFMU) Network, consisting of fourteen clinical centers, the Biostatistical Coordinating Center (BCC) and the NICHD, and is administered under cooperative agreements between each of the centers and the NICHD. Each of the funded institutions is represented by a Principal Investigator. A complete description of the organization of the MFMU Network is provided in the MFMU Network Policy Manual.

7.1.1 Participating Clinical Centers

The participating Principal Investigators of the clinical centers have agreed to abide by the study protocol, to have comparable staff, facilities and equipment and to ensure the proper conduct of the study at each of their centers including: recruitment and treatment of patients as specified in the protocol, accurate data collection and the transmission of information to the Steering Committee.

7.1.2 Biostatistical Coordinating Center

The BCC is responsible for all aspects of biostatistical design, data management, interim and final statistical analyses, and preparation of publications based on the study results. The Principal Investigator of the BCC reports to the Steering Committee and the Data and Safety Monitoring Committee.

7.1.3 NICHD

In addition to its role as funding agency, the NICHD participates in the activities of the Network, including the development of protocols, administration and conduct of the studies and preparation of publications.

7.1.4 Network Advisory Board

Appointed by the NICHD, the members of the Network Advisory Board consist of a group of experts who are not affiliated with research being conducted by the Network and represent the disciplines of maternal-fetal medicine, neonatology and biostatistics/epidemiology. The role of the board includes the review and prioritization of proposed studies, in addition to the identification of scientifically and clinically important questions and ideas that might be conducted by the Network. The NICHD Program Scientist convenes and attends the meetings.

7.2 Committees

7.2.1 Steering Committee

This committee consists of seventeen members. The Principal Investigator from each of the fourteen clinical centers, the BCC, and the NICHD MFMU Network Program Scientist are all voting members. The Chair of the Steering Committee may vote to break a tie. The Chair, a person independent of the participating institutions, is appointed by NICHD. The Steering Committee has the responsibility for identifying topics for Network studies, designing and conducting study protocols and monitoring study implementation, recruitment and protocol adherence. The committee receives recommendations from the Data and Safety Monitoring Committee and the Network Advisory Board.

7.2.2 Protocol Subcommittee

The subcommittee consists of a chair (who is an investigator from one of the clinical centers), investigators from one or more other clinical centers, BCC staff, nurse coordinators, outside consultants

(if appropriate), and the NICHD Network Program Scientist. The Protocol Subcommittee is responsible for the preparation and conduct of the study, and reporting the progress of the study to the Steering Committee.

